Parenteral nutrition is made up of amino acids, dextrose, intravenous fat emulsion (IVFE), micronutrients, fluids, and electrolytes. In addition to the patient-related factors listed above which are known to contribute to the development of PNAC, the IVFE component of PN, and specifically soybean-based emulsions, have been shown to be an independent causative factor in the development of PNAC.^{14,15} Soybean-based fat emulsions contain high levels of phytosterols which have been shown to impair bile drainage and contribute to hepatobiliary dysfunction.¹⁶ Given these findings, several strategies have been undertaken to minimize the effects of IVFE on the liver; these strategies include soybean-based IVFE reduction or the use of alternative IVFE such as marine oil-based emulsions or combination fat emulsions. Data supporting these approaches, however, have been based on retrospective or uncontrolled studies thus limiting the strength of the supporting evidence. Further, soybean based fat emulsions remain the only approved IVFE products for use in pediatric patients in the United States.

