This is a multi-institution, prospective, randomized study evaluating IVFE dose reduction on the development of PNAC as a proxy measure of PNALD in neonates requiring prolonged PN. The definition of PNAC will be that used predominantly in the literature – a direct bilirubin level of ≥ 2 mg/dL, documented on two occasions 1 week apart, in patients who have required parenteral nutrition for more than 2 weeks. **Eligible neonates will be randomized into two treatment arms: standard IVFE administration (3 g/kg/day) or IVFE reduction (IFER) (1 g/kg/day).** A total of 60 subjects (30 subjects per arm) will be included in the study. The study will evaluate

short- and long-term outcomes of this strategy. In the short-term, infants will be followed for up to 12 weeks for the development of PNAC. If a subject's PN is discontinued before 12 weeks, and if they remain in the hospital, follow-up data will be collected for an additional 7 days but not beyond a total of 84 days. Only standard-of-care data will be collected during these 7 days. No procedures will be performed for the purpose of this study during these 7 days. In the long-term, subjects' neurodevelopmental outcomes will be assessed at 12 and 24 months corrected gestational age (± 2 weeks).

Primary outcome measure:

1. The rate of rise of direct bilirubin as a function of time (mg/dL/week) between the two groups over 12 weeks or until the subject has been off of PN for >7 days, whichever comes first.

Secondary outcome measures

1. Initial 12 week period:
 - a. The incidence of PNAC (direct bilirubin ≥ 2 mg/dL) and severe PNAC (direct bilirubin ≥ 4 mg/dL in subjects on parenteral nutrition for at least 2 weeks)
 - b. The time to development of PNAC and severe PNAC
 - c. The peak total and direct bilirubin levels
 - d. The incidence of EFAD
 - e. Adequacy of growth as evaluated by z-scores for weight, height, and head circumference
 - f. Other safety measures assessed during the initial 12 week period will include adverse events (e.g., episodes of sepsis and catheter-related blood stream infections).
2. Long-term follow-up:

Neurodevelopmental assessments will include:

 - a. At 12 months corrected gestational age (± 2 weeks):
 - i. Bayley Scales for Infant and Toddler Development (BSID-III)
 - b. At 24 months corrected gestational age (± 2 weeks):
 - i. Bayley Scales for Infant and Toddler Development (BSID-III)
 - ii. MacArthur-Bates Communicative Development Inventories (CDI)

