Descriptive statistics using standard statistical tests (e.g. Student's t-test, paired sample t-test, Wilcoxon rank sums tests, Fisher's exact tests, Chi-square test, McNemar's test, etc.) will be used throughout the statistical analysis of data. Logistic regression will be used to compare differences between groups. Because septicemia can exacerbate PNAC, we will include the incidence of septicemia as a covariate in our analysis. Septic episodes will be defined as positive cultures or clinical presentation consistent with sepsis during the 7 day period corresponding to the subject's weekly bilirubin value. The number of septic episodes will be accounted for using a Poisson regression analysis (or possibly a negative binomial regression if there is more variability than expected for a Poisson distribution), with the total time on PN as an offset, allowing us to compare the rate of occurrence of septic episodes in the two groups.

Primary Outcome Measure

The primary outcome measure – change in direct bilirubin as a function of time (mg/dL/week) between the two groups – will be evaluated using a linear mixed model analysis to compare the slope of total bilirubin levels between the standard and reduced groups. This model will allow us to examine the degree of variability between subjects in the rate of change over time, and will take this variability into account in the model by including a random effect for the slope of time for each subject as well as a random intercept for each subject.

Secondary Outcome Measures

1. Time to PNAC (direct bilirubin ≥ 2 mg/dL) and time to severe PNAC (direct bilirubin ≥ 4 mg/dL)

The time to development of a first occurrence of PNAC and of severe PNAC will be evaluated using survival analysis. Initially, we will compare the two groups using Kaplan-Meier curves, but the eventual analysis will take into account important covariates, such as development of sepsis, average IVFE dose and percentage of calories from enteral feeds using a Cox proportional hazards survival analysis. We will test whether the proportional hazards assumption is met for the analysis by including an interaction term between treatment group and time to see if any differences between the groups are consistent or increase/decrease over time. The effect of important time-varying covariates (e.g., septic episodes) can also be taken into account using a Cox model.

2. Level of peak total and direct bilirubin

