These measures will be compared between the two treatment groups using a linear mixed model.

3. Incidence of PNAC, severe PNAC, and EFAD

The number of occurrences of each of these outcomes will be compared using either a Poisson regression model or a negative binomial model if the variance in these counts is greater than expected for a Poisson distribution. We will also include the time on TPN as an offset, so that we can compare the rates of occurrence of each of these outcomes for the two treatment groups. These regression models will be adjusted for the covariates such as development of sepsis, average IVFE dose, and percentage of enteral feeds.

4. Adequacy of growth as evaluated by z-scores for weight, height and head circumference

The z-scores for each of these measures will be compared between the two treatment groups using a linear mixed model. For normally growing infants, we would expect that there would not be a trend in z-scores because we would expect them to maintain their curve. However, for the subjects in this study, there may be a loss in z-score over time due to inadequate growth. The slopes of the changes in these z-scores over time will be compared between the two treatment arms. A random intercept will be included for each subject to allow for individual variability in average values as well as a random slope to allow for variability in the rate of change over time across subjects. Important covariates, such as gestational age (<32 weeks gestation vs. ≥32 weeks gestation) and birth weight will also be used as covariates in this analysis.

5. Neurodevelopmental Outcomes

Bayley Scales of Infant and Toddler Development (BSID-III):⁴⁵ Raw scores are converted to composite and subscale scores using age-standardized norms. Scale composite average internal consistency reliability coefficients range from .91 to .93 with subtest reliability ranging from .86 to .91. Validity-related studies indicate relatively high correlations (.72-.79) with the Wechsler Preschool and Primary Scale of Intelligence – Third Edition (WPPSI-III)⁵³ and with the Preschool Language Scale – Fourth Edition (PLS-4)(.71-.83).⁵⁴

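### The models named for PNAC, severe PNAC and EFAD adjust the arm comparison for delivered lipid dose, sepsis and enteral feeding, so their arm coefficient is not the effect of assignment

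*Combined protocol and SAP*

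**What the plan says.** Study Design defines the arms by lipid dose: "standard IVFE administration (3 g/kg/day) or IVFE reduction (IFER) (1 g/kg/day".

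Under Secondary Outcome Measures, item 1 covers time to PNAC and severe PNAC. Its first step is unadjusted: "Initially, we will compare the two groups using Kaplan-Meier curves". A Cox model follows as the later and adjusted step, and of this step the plan says that "the eventual analysis will take into account important covariates, such as development of sepsis, average IVFE dose and percentage of calories from enteral feeds". Item 3 (incidence of PNAC, severe PNAC and EFAD) uses Poisson or negative binomial models with time on PN as offset: "These regression models will be adjusted for the covariates such as development of sepsis, average IVFE dose, and percentage of enteral feeds". Arm stays in both. Item 1 tests a group-by-time interaction, and item 3 compares event rates between the two groups.

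The opening of Planned Statistical Analysis adds, without naming an outcome, "Because septicemia can exacerbate PNAC, we will include the incidence of septicemia as a covariate in our analysis". It also lists common two-group tests and says "Logistic regression will be used to compare differences between groups". Potential Confounding Variables adds mean dose, duration of IVFE/IFER and enteral intake as general adjustments. Planned Statistical Analysis and the Intent to Treat paragraph describe all analyses as intent to treat.

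**The concern.** A randomised comparison estimates the effect of assignment when the model holds arm and, if wanted, variables fixed before randomisation. Average IVFE dose is assigned dose as actually given. With it beside arm, the arm coefficient compares infants from different arms who received the same lipid. That is a different question, and few infants can inform it.

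Study Significance/Background says soybean-based emulsions "have been shown to be an independent causative factor in the development of PNAC". If so, the effect of assignment runs through delivered dose, and holding dose fixed removes the effect that the trial looks for.

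Sepsis and feeding also follow randomisation. Septic episodes are themselves compared between arms ("allowing us to compare the rate of occurrence of septic episodes in the two groups"), and the inpatient team is unblinded, so feeding can follow arm.

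At stake are PNAC incidence, the only secondary outcome with its own sample-size calculation, and time to PNAC, the first secondary hypothesis. A real effect could be reported as null.

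**Working it through.** **1. Inputs from the documents.** PNAC 50% against 10%, alpha 0.05 (taken as two-sided), 80% power, 23 per group (Sample Size Determination); 30 per arm (Study Design).

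**2. Reproducing the plan's figure.** Unadjusted exact power is the sum over a and b of Bin(a; n, 0.50) × Bin(b; n, 0.10), taken over tables with Fisher p ≤ 0.05.

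- n = 22: 78.6%
- n = 23: 81.1%
- n = 30: 91.4%

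So 23 is the smallest n above 22 to reach 80%, and the stated size matches a comparison with no covariates.

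**3. Assumptions on dose.** The documents give no spread of average dose. Within-arm SDs (standard/IFER) are taken as 0.3/0.1, 0.5/0.2 or 0.8/0.3 g/kg/day. Mean-dose gaps are 2 (3 − 1), 1 (2 − 1, the low end of the 2–3 g/kg/day in the sample-size section) and 1.5 (between, because the standard arm starts at 1 and steps up).

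**4. Overlap of arm and dose.** With equal arms, variance inflation = 1 + (gap/2)² ÷ mean within-arm variance.

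- Example, gap 2, SDs 0.3/0.1: mean variance (0.09 + 0.01)/2 = 0.05, so 1 + 1/0.05 = 21.0. The standard error of the arm term grows about √21 = 4.6 times (a linear-model guide).
- Across the three SD pairs: 21.0, 7.9, 3.7 (gap 2); 12.2, 4.9, 2.5 (gap 1.5); 6.0, 2.7, 1.7 (gap 1).

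**5. Simulated power for the arm term.** 30 per arm, risks held at 50% and 10%, normal doses, two-sided Wald test at 0.05. Poisson count model (5,000 trials per scenario) with model-based or robust standard errors; Cox model (4,000 trials) with constant hazard from week 2 to week 12 and dose averaged up to the event. Only dose is added; sepsis and feeding are not.

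Arm only: count 86–88% (model-based) or 92–94% (robust); Cox 93–94%.

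Dose added, effect acting through delivered dose (all gaps and SDs): count 1–2% (model-based) or 6–9% (robust); Cox 3–5%.

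Dose added, risk depending on arm only (the reading kindest to the plan), for the three SD pairs in order:

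| Gap | Count, model-based | Count, robust | Cox |
|---|---|---|---|
| 2 | 8 / 21 / 41% | 26 / 41 / 60% | 18 / 34 / 54% |
| 1.5 | 14 / 34 / 53% | 34 / 54 / 69% | 27 / 46 / 66% |
| 1 | 29 / 50 / 67% | 49 / 66 / 79% | 42 / 63 / 78% |

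**6. Checks.**
- With PNAC at 40% in both arms, the dose-adjusted models reject in about 1% (count, model-based), 5–8% (count, robust) and 5–6% (Cox). The second scenario in step 5 is therefore at about each test's own false-positive rate.
- Count-model trials with no event in an arm (3.6–5.0%) were skipped. Counting them as non-rejections lowers unadjusted power by about 4 points and adjusted power by at most about 3.
- Adding a time-on-PN offset (uniform 4–12 weeks, assumed) moves the figures by about 2 points or less.

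**7. Averaging window.** None is defined. Sustained direct bilirubin of 2.5 mg/dL or more changes the dose (Study Arms), and EFAD raises it (EFAD section). An average that runs past the event is partly a result of the outcome.

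**The case against.** **Unadjusted comparisons are in the plan.** Kaplan-Meier curves, Fisher and chi-square tests and a logistic regression are all mentioned, and the 23 per group matches a Fisher test. This stands in part. A reader might infer that the adjusted models are the only or final analysis of incidence. The text does not say so: only the Cox model is called eventual. But no unadjusted or baseline-adjusted test is assigned to PNAC or EFAD, no log-rank test is named, and nothing says which result counts.

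**Intent to treat may mean only who is analysed, and in which arm.** On that reading the commitment is kept, and it would be too strong to call it broken. The misfit is in what the coefficient estimates; including every infant does not change that.

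**These are secondary outcomes.** This stands and limits the severity. Apart from PNAC incidence, the sample-size section uses them only to establish trends.

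**The simulations are stylised.** This stands for their precision. The SDs are assumed, only dose is added, and uncapped normal doses put half of the standard arm above its 3 g/kg/day maximum at gap 2. Capping lowers adjusted power further (from 41% to 27% at gap 2, SDs 0.8/0.3, model-based), so the direction holds.

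**Dose, sepsis and feeding are confounders.** They are not confounders of a randomised arm contrast, because they largely accrue after assignment. Exploratory models may still use them.

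**Conclusion.** The concern holds for the secondary outcomes and should be fixed. As written, the Cox model for time to PNAC and severe PNAC, and the only models named specifically for incidence of PNAC, severe PNAC and EFAD, do not give the effect of assignment. The 23 per group does not describe the adjusted model. No single power figure follows from the documents: the loss ranges from moderate to nearly complete, depending on dose spread, dose gap, type of standard error and whether the effect acts through dose. Sepsis and feeding are not quantified. Nor is EFAD, because the standard arm is profiled only after lipid restriction; the plan also expects EFAD to be very rare.

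Three stronger readings are not supported:

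- *The primary slope analysis is compromised too.* Its own paragraph names no covariate. The sepsis, dose and feeding sentences elsewhere are general, so this is a question to clarify.
- *The adjustment inflates false positives.* With averaging stopped at the event, the Cox model rejects in 5–6%. Later averaging could create a false difference, but its size depends on a window and switch rate that the documents do not give.
- *The neurodevelopmental analysis is wrong.* EFAD, and bilirubin if measured after randomisation, may lie on the treatment pathway; no more than that is shown.

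**What to change.** - For PNAC, severe PNAC and EFAD, state that the treatment effect comes from models with arm and pre-randomisation factors only: the gestational-age stratum, centre where numbers allow (randomisation is within centre), and baseline direct bilirubin for the PNAC outcomes. Leave out average dose, duration of IVFE/IFER, sepsis and enteral feeding.
- Time on PN may stay as the offset, with a note that it is post-randomisation and a sensitivity analysis without it.
- Keep the dose, sepsis and feeding models as labelled exploratory analyses, with dose averaged only up to the event.
- As a clarification, state that the general covariate sentences in Planned Statistical Analysis and Potential Confounding Variables do not apply to the primary slope comparison.
- For neurodevelopment, also report an arm comparison without EFAD and post-randomisation bilirubin.

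The cost is analysis wording. No new data are needed, and every exploratory model can still be run.

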3. Weight, gestational age at the time of enrollment/randomization, and weekly thereafter
4. Inclusion diagnosis
5. Number of septic episodes according to standard definitions³⁸
6. Use of choleric medications
 - a. Ursodiol
 - b. Cholecystokinin
 - c. Phenobarbital
7. Nutritional data
 - a. Parenteral nutrition data
 - i. IVFE dose
 - ii. Dextrose infusion rate
 - iii. Total calories and % calories obtained via PN
 - b. Enteral nutrition data
 - i. Total calories and % calories being obtained via enteral route
 - ii. % calories obtained via breast milk
8. Growth parameters (whenever possible, obtain all growth measurements on the same day of the week)
 - i. Weight (with z-score) weekly (every 7 days ± 2 days)
 - ii. Height (with z-score) weekly (every 7 days ± 2 days)
 - iii. Head circumference (with z-score) weekly (every 7 days ± 2 days)
9. Additional safety data to be obtained from human subjects is summarized below, indicating any key differences in frequency of monitoring between the two groups:

Laboratory Parameter	Frequency (+24 hours)*
Fractionated bilirubin panel (includes total, indirect, and direct bilirubin)	One time weekly (Monday)
Serum bile acids (total)	One time monthly (every 4 th Monday on treatment)

Point of care or serum glucose measures	- Daily for the first 5 days of PN, then twice weekly (Monday, Thursday) - Confirmatory test if serum glucose is >150 mg/dL on electrolyte panel
Serum Triglycerides	One time weekly (Monday)
Essential Fatty Acid Profile	IFER Group: Every 2 weeks (Thursday) Standard Group: At the time of restriction of IVFE to 1 g/kg/day three days per week, then every 2 weeks (Thursday)
Comprehensive metabolic panel	Twice weekly (Monday, Thursday)
Magnesium level	Twice weekly (Monday, Thursday)
Phosphorus level	Twice weekly (Monday, Thursday)
Complete blood count	One time weekly (Monday)

* Lab draw volumes will be below each institution's daily limits

Definition of Sepsis

Sepsis will be defined in a standard manner using the following criteria (**Table 2**):³⁸

The presence of at least two of the following four criteria ***in the presence of or as a result of suspected or proven infection***:

1. Core temperature of >38.5C or <36C

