All adverse events will be graded as follows in their relation to IFER: definitely not related, unlikely to be related, possibly related, definitely related or insufficient information. All cases rated as possibly or definitely related will be defined as an SAE. These SAEs will be reported to the University of Michigan Sponsor-Investigator within 48 hours. The site PI will be contacted immediately and the case will be evaluated for reporting to IRB, FDA and study termination, if deemed necessary. Each clinical site will report SAEs to their local IRB as per their standard reporting policy. As per 21 CFR 312.32(c), the sponsors will also notify FDA and all participating investigators in an IND safety report of any adverse experience associated with the use of the drug that is both serious and unexpected.

Data Safety Monitoring Board

An independent data safety monitoring committee will be established to monitor the study for safety and to determine if a statistical difference has been achieved between the two groups for the primary outcome measure at interim data analyses. The data safety monitoring committee will review the data at the halfway point of the study to assess the safety and efficacy of the study to that point. If safety issues are revealed the study investigators and each site's IRB will be notified immediately. The data safety monitoring committee will also ensure that adverse events are promptly reported to the FDA, and all participating investigators will be notified as well of any adverse experience associated with the use of the drug that is both serious and unexpected.

Sample Size Determination

The sample size was calculated for the primary outcome (rate of rise of direct bilirubin) using previously published data as well as our clinical experience.^{22,23} We have assumed that the mean bilirubin levels at baseline, 4 weeks, 8 weeks and 12 weeks in the standard dosing group (2-3 g/kg/day) will be 0.55 mg/dL, 1 mg/dL, 1.5 mg/dL and 2 mg/dL corresponding to a slope of 0.125 mg/dL/week over 12 weeks. The standard deviation of the bilirubin measures at each of these four time points is 1. Likewise, we have estimated that the mean bilirubin levels at baseline, 4 weeks, 8 weeks and 12 weeks in the minimization group (1 g/kg/day) will be 0.45 mg/dL, 0.5 mg/dL, 0.45 mg/dL and 0.5 mg/dL (a slope of roughly zero). The standard deviation of the bilirubin measurements at

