each of these four time points is 1. The correlation of any two adjacent measures on the same individual is 0.5. This correlation drops to 0.354 between baseline and 8 weeks and to 0.25 between baseline and 12 weeks.

Using the above assumptions, a sample size of 15 subjects per group using a repeated measures ANOVA will have 85% power to detect the change in slopes as being significant at the 0.05 level, 79% power to detect a difference in means overall between groups and 88% power to detect the general change in means over time across the two groups. When the sample size is increased to 20 subjects per group, the above power numbers increase to 95%, 90% and 96%, respectively. If 30 subjects are recruited per group this design will allow for a 33% attrition rate by twelve weeks as we expect that not all patients will require PN for the full 12 weeks of the initial study period. Thus, we will recruit a minimum of 30 subjects per group to ensure adequate power to detect our primary outcome measure.

Of the secondary outcomes, sample size was also calculated for the incidence of cholestasis. Assuming an incidence of 50% in the standard group and an incidence of 10% in the minimization group, with $\alpha = 0.05$ and power of 80%, a sample size of 23 is required for each group. Regarding the other secondary outcomes, our sample size is large enough to allow for establishing trends which may then highlight avenues for future research.

Planned Statistical Analysis

All data analysis will be directed and performed by a statistician through the Center for Statistical Consultation and Research at the University of Michigan (<http://cscar.research.umich.edu/about/>). Data will be analyzed using SAS software release 9.3 for Windows (Copyright, SAS Institute Inc., SAS and all other SAS Institute Inc. product of service names are registered trademarks or trademarks of SAS Institute Inc., Cary, NC, USA). All study subjects will be included in the statistical analysis in an intent-to-treat manner.

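### Peak bilirubin, one value per infant, is assigned to a linear mixed model with no random effect, scale or covariates; by default this is an untransformed two-group comparison, inefficient if peaks are right-skewed

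*Combined protocol and SAP*

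**What the plan says.** Study Design lists "The peak total and direct bilirubin levels" among the secondary outcomes of the first 12 weeks. Planned Statistical Analysis, Secondary Outcome Measures, item 2 ("Level of peak total and direct bilirubin") gives the analysis in one sentence: "These measures will be compared between the two treatment groups using a linear mixed model". It names no random effect, repeated factor, covariate, scale or transformation.

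Where data do repeat within infant, the plan is specific: the primary outcome and the growth z-scores each have a random intercept and a random slope over time. The opening of Planned Statistical Analysis lists the t-test and the Wilcoxon test among standard methods but assigns neither to the peak.

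Sample Size Determination gives no distribution, SD or power for the peak. Its inputs for individual bilirubin measurements are, for the standard arm, means that "will be 0.55 mg/dL, 1 mg/dL, 1.5 mg/dL and 2 mg/dL corresponding to a slope of 0.125 mg/dL/week over 12 weeks", and for the reduced arm means of 0.45, 0.5, 0.45 and 0.5 mg/dL. For both arms the SD is 1 at every visit; for the standard arm it reads: "The standard deviation of the bilirubin measures at each of these four time points is 1".

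**The concern.** There are two separate issues.

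First, the named method does not fit the data structure. With one peak per infant there is nothing for a subject-level random effect to estimate, and no other grouping is named. Two analysts could follow the sentence and run different analyses.

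Second, the scale is left open. If bilirubin is right-skewed, a few infants with very high peaks dominate the arm mean and its standard error in mg/dL, and a real shift in the bulk of infants can be missed. The Background reports that a retrospective cohort of surgical infants found lower peak direct bilirubin with lipid reduction (p<0.0001), so readers will look for this result. Choosing between mg/dL, log and rank analyses after seeing the data would invite selection.

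**Working it through.** **1. The plan's own figures.** None is stated for the peak, so I checked that the neighbouring inputs are understood.
- Incidence of cholestasis: "Assuming an incidence of 50% in the standard group and an incidence of 10% in the minimization group", with "power of 80%, a sample size of 23 is required for each group". Fisher's exact test, two-sided 0.05 (sidedness assumed), has 81.1% power at 23 per group. This agrees.
- Overall difference in means, from the stated means, SD 1 and correlations 0.5, 0.354 and 0.25 (noncentral t): 79.6% at 15 and 90.2% at 20 per group, against 79% and 90% stated. This agrees.

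**2. Structure.** With one row per infant the model is y_i = a + b·arm_i + u_i + e_i. The variance of y_i is var(u) + var(e), and only the sum can be estimated. In a test data set, ordinary least squares gave an arm difference of -1.519 with residual variance 2.931. The mixed model with an infant intercept gave the same difference, split the variance into 1.465 + 1.465, and reported a Hessian that was not positive definite. Its standard error (0.399, against 0.443 from least squares) is therefore not to be relied on. A random centre intercept could be fitted; there it was estimated at essentially zero and returned the least-squares result.

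**3. Skew implied by the inputs.** A normal distribution with mean 0.5 and SD 1 puts Φ(-0.5) = 31% below zero, which is impossible for bilirubin. For the standard arm at 12 weeks (mean 2, SD 1) the figure is Φ(-2) = 2.3%, so the argument is strong for the reduced arm and for early visits, and weak for late standard-arm visits.

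**4. Power for the peak.** Peak = maximum of the four planned visits, with the plan's means, SD and correlations; two-sided 0.05; thousands of simulated trials per setting. Lognormal margins: σ² = ln(1 + SD²/mean²), μ = ln(mean) - σ²/2. Gamma margins: shape = mean²/SD², scale = SD²/mean. The two lognormal rows differ in whether the stated correlations are applied to the logs or to the mg/dL values.

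| Margins | n per arm | t-test, mg/dL | t-test, log | Wilcoxon | Loss, mg/dL vs log |
|---|---|---|---|---|---|
| Lognormal (correlation on logs) | 30 | 87% | 100% | 99.9% | 13 |
| Lognormal (correlation on mg/dL) | 30 | 90% | 100% | – | 10 |
| Gamma | 30 | 87% | 99.9% | 99% | 13 |
| Lognormal (correlation on logs) | 20 | 81% | 99.6% | 99% | 19 |
| Lognormal (correlation on mg/dL) | 20 | 83% | 99.8% | – | 17 |
| Gamma | 20 | 76% | 99% | 95% | 23 |
| Near-normal | 20 | 95% | 90% | 94% | none (log is 5 lower) |

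The 30 and 20 per arm are the plan's recruitment target and the number left after its 33% attrition. An infant who leaves PN early still has a peak, so 30 is the more natural figure and 20 the cautious one.

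**5. Is the lognormal assumption reasonable?** With correlations on the logs it gives a peak of at least 2 mg/dL in 51% and 12% of infants, close to the plan's 50% and 10% for cholestasis. The match is rough, because the Study Design definition of PNAC needs two readings a week apart.

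**6. Sensitivity.** Lognormal peaks, 30 per arm, with P(peak ≥ 2 mg/dL) set to 43% and 22% as in the cited retrospective cohort: the loss is 5, 18, 24 and 31 points at log-SD 0.5, 1.0, 1.2 and 1.5. The most extreme setting tried (50% against 25%, log-SD 1.5) gave 38.4% against 74.0%, a loss of 35.6 points. Type I error in mg/dL was 2.9% to 4.3% at log-SD 1.5 to 0.8, so slightly conservative and not inflated.

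**The case against.** The strongest reply is that this is one under-specified sentence for a secondary outcome, for which Sample Size Determination promises only trends. No stated power is undermined, and with the plan's inputs the mg/dL comparison still has about 87% to 90% power at 30 per arm. That stands, and it limits the weight of the point.

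A mixed model could also have content: the trial is multi-centre with randomisation within centre, and total and direct peaks could be modelled jointly. Neither is written, so the fair charge is that the model is unspecified, not that no mixed model could be used.

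The log test is favoured by construction when peaks are lognormal. In part this stands, but gamma margins show a similar loss, and the Wilcoxon test, which assumes neither, recovers most of it. The log scale is not ideal either: under the lognormal inputs the log-SDs of the peak differ between arms (about 0.49 and 1.08). The simulations compare unadjusted tests; the adjusted regression proposed below was not itself simulated.

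A reader might infer that a maximum must be more skewed than the visits it is taken from. That is not so here: with gamma margins in the reduced arm the peak has skewness of about 2.6, against 2·SD/mean = 4.0 to 4.4 at the visits. The point does not need that step.

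**Conclusion.** The point holds as a low-cost improvement. The sentence does not define a reproducible analysis, and its default reading is an untransformed two-group comparison. If peaks are right-skewed as the planning inputs suggest, that comparison gives up about 10 to 13 points of power at 30 per arm and about 17 to 23 at 20 per arm. This rests on lognormal or gamma margins, the plan's means, SD and correlations, and a peak taken over four visits although bilirubin is drawn weekly.

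Three stronger readings are tempting and are not supported:
- That the mixed model itself costs power. It does not; with one row per infant it gives the ordinary arm difference, and the loss comes from the scale.
- That the plan commits to mg/dL or describes the peak as skewed. It states neither a scale nor a distribution; both are inferences.
- That some 20 points is an upper limit. The loss runs from nil with near-normal peaks to about 36 points at the most extreme setting tried.

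**What to change.** Replace the sentence under item 2 with a linear regression of log peak bilirubin, direct and total separately, on:
- treatment arm;
- log pre-randomisation bilirubin. A first on-study value after randomisation should not be used: it may already reflect treatment and is itself one of the values from which the peak is taken;
- the randomisation strata: gestational age (<32 against ≥32 weeks) and centre, with centre as the random effect if a mixed model is kept.

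Report the ratio of geometric means with a 95% interval. Fix in advance a floor for values below the reporting limit. Name the Wilcoxon test, already among the plan's listed methods, as the sensitivity check.

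The cost is a few lines of text. Eligibility already depends on direct bilirubin never having exceeded 2 mg/dL, so a pre-randomisation direct value should usually exist. The laboratory schedule does not list a baseline draw, so the plan should say which pre-randomisation values are used and what is done if one is missing. The downside is that the effect becomes a ratio and not a mg/dL difference; medians in mg/dL by arm should be reported beside it.
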